#### **Authors' contributions:**

MHD designed the protocol, recruited patients, collected data, coordinated the study and will write the manuscript. CR and PAB recruited patients and collected data. MS helped with protocol design. FL supervised the whole process and will review the manuscript.

**Amendments:** sample size enlargement from 15 to 30 patients (July 2017)

#### **Support:**

No financial support was obtained for this study.

July 13th 2017

## 1. INTRODUCTION

### 1.1 Rationale

Oxygen is one of the most widely used drugs in acute care settings, with 34 % and 13,8 % of patients receiving some in ambulances and in hospitals, respectively [1, 2]. It is used to correct hypoxemia (35 %), and to relieve chest pain (35%) and dyspnea (40%)[3], even if numerous studies demonstrate that oxygen has no use in treating respiratory distress in normoxic patients [3-5]. Interestingly, a prescription is found for oxygen therapy in only 55 % of cases, with a saturation target specified in barely 52 % of those[2].

While hypoxemia seems to be a daily preoccupation for health care professionals, oxygen therapy carries some risks, which have been known for more than 60 years[6]. It is the pulmonary consequences of hyperoxia that have been studied the most. Of note, airway inflammation and cellular lung damage through reactive oxygen species production have been related to hyperoxia. In COPD patients, the risk of hyperoxia-induced hypercapnia has led international guidelines to recommend a target peripheral oxygen saturation of 88-92 % in these patients[5, 7, 8], but they are still receiving too much oxygen.

Obese people are also at risk for hyperoxia-induced hypercapnia[5, 7], but literature is sparse. Obesity is defined by WHO as a body mass index (BMI) superior to 30 kg/m^2, affecting more than 600 million adults in 2014, a number that had doubled since 1980 and corresponded to 13 % of world population [9]. In Canada, 28,7 % of women and 26,8 % of men were obese, percentages as high as 34,8 % and 33,6 % respectively in the United States [10]. Obesity-hypoventilation syndrome (OHS), originally named Pickwickian syndrome, is defined by the combination of obesity and daytime hypercapnia ( $\text{PaCO}_2 > 45 \text{ mmHg}$ ) after exclusion of other causes [11, 12]. It is found in 10 to 20 % of obese patients treated in sleep disorders clinics and in 50% of hospitalized obese patients having a BMI higher than 50 kg/m^2 [11, 13, 14]. Several pathophysiologic mechanisms belonging to respiratory centers, ventilator mechanics and sleep-disordered breathing have been proposed. Kaw and al. Have recently

shown that obese patients with obstructive sleep apnea syndrome (OSA) meeting the criteria for OHS were at increased risk for postoperative complications-respiratory or heart failure, intubation, ICU transfer, prolonged hospital stay- than those with isolated OSA [15]. Now, concerning the effect of hyperoxia, Wijesinghe and al. have shown that, in stable OHS patients, breathing a  $\text{FiO}_2$  of 100 % for 20 minutes leaded to an elevation in  $\text{PtCO}_2$  of 5 mmHg compared to ambient air. Moreover, 43,5 % of patients had majored their  $\text{PtCO}_2$  of more than 4 mmHg while breathing a  $\text{FiO}_2$  of 100% and the study had to stop in 3 patients because of a worrisome rise of more than 10 mmHg [16] . Hollier and al. have compared the effects of  $\text{FiO}_2$  of 28% and 50 % on a 20 minutes time lapse, but observed a smaller  $\text{pCO}_2$  difference [17]. Recent international practice guidelines recommend a  $\text{SpO}_2$  target of 88-92 % in morbidly obese patients ( $\text{BMI} > 40 \text{ kg/m}^2$ ), but do not address this matter for obese patients with a lower BMI [5, 7]. In light of contemporary available evidence, many questions remain unanswered. What is the effect of hyperoxia on obese patients in an acute setting? Is there, in obese patients not previously known for OHS, a risk of hyperoxia-induced hypercapnia in this clinical context?

## **1.2 Objectives and hypotheses**

This study aimed to evaluate the risk of hyperoxia-induced hypercapnia in obese patients after coronary artery bypass grafting, by comparing a  $\text{SpO}_2$  target  $\geq 95 \%$  achieved by manual titration (usual care) and a more conservative target of 90 % achieved by automatic titration in the post-extubation period.

## **2. METHODS**

15 obese patients will be recruited at Quebec's heart and lung Institute. Informed written consent will be obtained from each included patient. The protocol will be submitted to the establishment's ethics committee for approval.

## **2.1 Inclusion criteria**

- Age  $\geq$  18 years
- BMI  $\geq$  30 kg / m^2
- Procedure: coronary artery bypass grafting (CABG) only
- SpO2  $\geq$  95% before extubation

## **2.2 Exclusion criteria**

- Comorbidities:
  - Chronic obstructive pulmonary disease
  - Cystic fibrosis
  - Restrictive syndrome other than that associated with obesity (interstitial lung disease, neuromuscular disease, etc.)
  - OSA requiring CPAP therapy
- No FreeO2 device available at the time of the study
- Patient enrolled in another study that does not allow co-enrollment

## **2.3 Sample size**

Since there are few data in the literature regarding the effect of hyperoxia in the obese population, and these data are for patients known to have hypoventilation syndrome and in the stable state, it is difficult for us to estimate the magnitude of the possibly observable change in PaCO2. Based on previous studies on stable OHS patients[16, 17], empirical sample size will be set at 15 patients to detect a PaCO2 difference of 5 mmHg between groups.

[figure not shown]

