### **3. AMENDMENT**

Analysis of the primary outcome after inclusion of 15 patients showed a trend towards a higher end-of-period  $\text{PaCO}_2$  in control mode, but the study lacked statistical power. We thus decided, following the recommendation of our statistician, to make an amendment to the protocol in order to enlarge sample size to 30 patients. This amendment was accepted by our institution's board on July 13th, 2017.

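### Does the 5 mmHg basis for 15 patients, with no new basis given for 30, leave the sample size in need of correction?

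*Protocol*

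**What the plan says.** Section 2.3 (Sample size) explains that published data are few and come from stable patients already known to have hypoventilation syndrome, so that "it is difficult for us to estimate the magnitude of the possibly observable change in PaCO 2". Citing two earlier studies, it continues: "empirical sample size will be set at 15 patients to detect a PaCO 2 difference of 5 mmHg between groups". It gives no SD, significance level or power.

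Section 1.1 (Rationale) describes both studies. In the first, an FiO2 "of 100 % for 20 minutes leaded to an elevation in" transcutaneous CO2 "of 5 mmHg compared to ambient air". The second compared FiO2 of 28% and 50% "on a 20 minutes time lapse, but observed a smaller" CO2 difference, whose size is not given.

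Section 2.4 sets the contrast for this trial: SpO2 of at least 95% by manual adjustment against 90 ± 2% by automatic titration, 30 minutes each, in a crossover. The primary endpoint (Section 2.6) is arterial PaCO2 at the end of each period.

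Section 3 (Amendment) reports a trend towards higher PaCO2 in control mode after 15 patients, "but the study lacked statistical power", and raises the number to 30 on the statistician's advice. Section 2 still reads "15 obese patients will be recruited at" the institute. The list of amendments at the front of the protocol records the change from 15 to 30.

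**The concern.** Three things look wrong together.

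- **The target is borrowed from a different setting.** 5 mmHg matches only the comparison of pure oxygen with room air, measured transcutaneously in patients with the syndrome. This trial compares two saturation targets in obese post-bypass patients who were not selected for it. The rationale itself says that the other cited study found less.
- **The two statements seem to clash.** If 15 patients were enough to detect 5 mmHg, it is odd to read later that 15 lacked power.
- **The figure of 30 has no stated basis.** No difference, SD or power goes with it, and 15 survives in Sections 2 and 2.3.

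At stake would be the reading of the result. With 30 patients a difference well below 5 mmHg could reach significance and be taken as meeting the design target, or a null result could be set against the wrong yardstick.

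**Working it through.** **Inputs.** From the protocol: difference δ = 5 mmHg; n = 15, then 30; each patient is his own control. Assumed, because the protocol does not give them: two-sided α = 0.05, paired t test, no dropout, and SD_d (the SD of the within-patient differences) between 4 and 10 mmHg.

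**Step 1: the plan's own figure.** Without SD, α or power, 15 can be neither reproduced nor refuted. One can only solve for the SD_d that it implies. Power is the probability that a noncentral t variable, with n − 1 degrees of freedom and noncentrality δ√n / SD_d, exceeds the critical value.

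- n = 15, 80% power: δ / SD_d = 0.778, so SD_d ≤ 5 / 0.778 = 6.43 mmHg. For 90% power, 5 / 0.901 = 5.55 mmHg.
- n = 30, 80% power: δ / SD_d = 0.529, so SD_d ≤ 5 / 0.529 = 9.45 mmHg. For 90% power, 5 / 0.612 ≈ 8.16 mmHg.

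Spending one more degree of freedom on a period effect hardly matters: the 80% limits become 6.39 and 9.44 mmHg.

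**Step 2: the range.** The smallest significant mean difference is t × SD_d / √n; for n = 30 this is 2.045 × SD_d / √30 = 0.373 SD_d.

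| SD_d (mmHg) | 4 | 6 | 8 | 10 |
|---|---|---|---|---|
| Power for 5 mmHg, n = 15 | 99% | 85% | 62% | 44% |
| Power for 5 mmHg, n = 30 | >99.9% | 99% | 91% | 75% |
| Detectable at 80% power, n = 30 (mmHg) | 2.1 | 3.2 | 4.2 | 5.3 |
| Smallest significant difference, n = 15 (mmHg) | 2.2 | 3.3 | 4.4 | 5.5 |
| Smallest significant difference, n = 30 (mmHg) | 1.5 | 2.2 | 3.0 | 3.7 |

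**Step 3: do the two statements clash?** A non-significant trend at 15 can arise in three ways, and none contradicts Section 2.3.

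- SD_d is larger than 6.43 mmHg. The protocol never claimed otherwise.
- The true difference is below 5 mmHg. With 2.5 mmHg as an illustration, power at n = 15 is 62%, 44% and 32% for SD_d of 4, 5 and 6 mmHg; at n = 30 it is 91%, 75% and 60%.
- Chance. With a true 5 mmHg and SD_d of 6 mmHg, 100% − 85% = 15% of 15-patient trials miss significance.

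Section 2.3 states an intention before the data; Section 3 reports what was seen.

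**Step 4: is the enlarged trial sized for 5 mmHg?** Yes, on these assumptions. Power is at least 91% for SD_d from 4 to 8 mmHg and stays at or above 80% up to 9.45 mmHg.

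**Step 5: how much weaker is the contrast?** The documents do not allow a figure. They give no expected FiO2 for either mode and no size for the smaller difference in the second cited study. Exposure is 30 minutes here against 20 in the cited studies, and the patients are newly extubated with postoperative narcotics recorded. A smaller effect than 5 mmHg is plausible, but its size is not shown.

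**The case for a change.** The strongest case for acting does not rest on the missing SD or α, which a statistical analysis plan may supply. It rests on what the protocol does state: a target taken from a non-comparable setting, and a doubling of the sample that never says which difference it serves. For SD_d of 4 to 8 mmHg the enlarged trial can declare significance at 1.5 to 3.0 mmHg, which is 30% to 60% of the only target in the document. Disclosing that a figure is weak does not make it suitable, and repair costs one paragraph and no patients.

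Much of this stands as description. 5 mmHg does match only the pure-oxygen study, the figure of 30 has no stated target, and neither number can be verified. The consequence does not follow. Section 2.7 analyses mean differences, and nothing in the protocol judges success against 5 mmHg. Significance below the planning difference is ordinary in any well-powered trial. The estimate and its confidence interval, whose half-width at n = 30 is the last row of the table, show what has been found or excluded.

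The obvious rewrite has its own traps. The factor 0.53 applies to SD_d; converting it with the within-patient SD would understate the detectable difference by √2, since 0.53 SD_d is about 0.75 within-patient SD. A version adjusted for the look at 15 would need a significance level that the protocol does not state. Deleting the 5 mmHg sentence would remove the record of how the trial was planned.

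**Conclusion.** No change follows. The protocol promises no power that the design fails to deliver. Fifteen patients suffice for 5 mmHg at 80% power if SD_d is at most 6.43 mmHg, and thirty if it is at most 9.45 mmHg (two-sided 5% paired t test, no dropout, before any adjustment for the look at 15). SD_d is not in the document, so these are limits and not a finding that either number was right.

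The 5 mmHg figure is a rough planning value, labelled empirical, and the protocol says that it comes from stable patients with the syndrome. The rise to 30 lacks a written rationale, but the number, reason and approval date are on record. Once the trial reports the observed SD of the differences and a confidence interval, readers need no planning figure to judge precision. The leftover 15 in Sections 2 and 2.3 is clerical, since the front-page list of amendments and Section 3 both give 30.

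Whether analysing the primary outcome at 15 and then extending affects the type I error is a separate question, which this conclusion does not settle.

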## **2.4 Study process**

We will compare the effect of two modes of oxygenation on capnia in post-CABG obese patients , immediately after extubation:

- A. FreeO2 mode : oxygen via nasal cannulas or mask (if O2 flow rate > 5 l / min for more than 5 minutes), automatically titrated by FreeO2 for a SpO2 of 90 ± 2%
- B. Control mode : oxygen via ventimask, manually adjusted by nurses for SpO2 ≥ 95% (routine care according to the local protocol in which extubation is done with a FiO2 equal to FiO2 before extubation + 10%).

Patients meeting all inclusion criteria will be randomized postoperatively. After being extubated, they will be oxygenated for 30 minutes according to FreeO2 or control mode, in a randomized order. They will then be oxygenated according to the second mode of administration for 30 minutes. Each patient will act as his own control (crossover design)(see figure 1).

**Figure 1** Study process

The study will last 1h for each patient, and should begin within 30 minutes after extubation. A resource person will be at the bedside for the duration of data

collection to ensure protocol compliance and integrity. We expect to be able to complete the data collection within a 12-month period.

## **2.5 Parameters collected**

The usual demographic data (age, sex, weight, height, BMI, waist size) will be collected during the recruitment of patients as well as the type of surgery (number of grafts, extracorporeal circulation duration), intraoperative and postoperative narcotic doses, left ventricular function and preoperative renal function. Continuous monitoring of oxygen flow, peripheral oxygen saturation and heart rate by FreeO2 will be achieved throughout both periods. During the control period, FreeO2 will collect data, but will not deliver oxygen. The respiratory rate will also be measured manually and on the monitor. When patients are oxygenated with FreeO2, they will record the flow of oxygen delivered; with the usual mode, we will note the FiO2 used. At the end of each period, hemodynamic measurements will be taken: heart rate, systemic arterial pressure, pulmonary artery pressure, vasopressor dosage. A total of four blood gases will be collected for each patient : a capillary blood gas the day before surgery (baseline), and arterial blood gases before extubation, after the first period and after the second period.

## **2.6 Outcomes**

The primary endpoint will be end-of-period PaCO2. Secondary endpoints will include end-of-period pH and PaO2 and percentage of time spent in hypoxemia (SpO2 <88%), in severe hypoxemia (SpO2 <85%) and in hyperoxemia (SpO2 > 96%). We will compare the respiratory rate data with 2 measurements (manual and monitor). We will also compare the hemodynamic data.

## **2.7 Statistics**

Mean differences will be used for all of the outcomes since they are continuous, taking into account the crossover design (analyses with four groups). Univariate and

multivariate analyses will be used to identify factors of response and nonresponse. Analyses to assess period, time and carryover effects will be done.

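### Is a mean difference the wrong measure for time spent in hypoxemia, when many patients may have none?

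*Protocol*

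**What the plan says.** Protocol Section 2.7 (Statistics) gives every outcome one effect measure and one reason: "Mean differences will be used for all of the outcomes since they are continuous". The section asks that the crossover design be respected and also promises analyses of period, time and carryover effects. It names no test, no interval and no distributional model.

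Section 2.6 (Outcomes) makes end-of-period PaCO2 the primary endpoint. The secondary endpoints include "percentage of time spent in hypoxemia (SpO 2 <88%), in severe hypoxemia (SpO 2 <85%) and in hyperoxemia (SpO 2 > 96"%).

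Section 2.4 (Study process) sets two 30-minute periods per patient. In one, oxygen is "automatically titrated by FreeO 2 for a SpO 2 of 90 ± 2"%. In the other it is "manually adjusted by nurses for SpO 2 ≥ 95"%. Section 2.1 requires a saturation of at least 95% before extubation. Section 3 (Amendment) records the decision to "enlarge sample size to 30 patients".

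No part of the protocol gives an observed or expected distribution for the times below 88% or 85%.

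**The concern.** The stated reason fits these two outcomes poorly. The lower edge of the FreeO2 band is 90 − 2 = 88%, which is 3 points above the severe cut-off. The control target is 10 points above it. Over 30 minutes, many patients may never fall below 85% in either mode, and few may fall below 88% in control mode. The data would then be a cluster of zeros with a few skewed positive values, and the mean of 30 such differences can hang on a handful of patients.

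The trial compares a lower saturation target with usual care, so time in severe hypoxemia is the natural counterweight to any gain in PaCO2. If the analysis were insensitive there, a real difference could be missed, or reported with too narrow an interval. The apparent remedy is to rank the within-patient period differences, compare the two randomized orders by a permutation test, and demote the mean difference to description.

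**Working it through.** **Does the text fix something wrong?** Section 2.7 fixes an effect measure. The mean within-patient difference in percentage of time estimates average time below the cut-off in one mode minus the other. That is defined and interpretable whatever the share of zeros; a bound at 0 or a mass at 0 does not bias it. Coverage and power are properties of a test or interval, and Section 2.7 specifies neither. That choice is commonly left to a statistical analysis plan, which is not at hand.

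**If the usual crossover t is assumed, how large is the loss?** There is no stated figure to reproduce, because the protocol sizes only PaCO2. The inputs are 30 patients (Section 3), with an assumed 15 per order. For each patient D = period 1 − period 2. The estimate is (mean D in order 1 − mean D in order 2)/2, its standard error is s_pooled × √(1/15 + 1/15)/2, and there are 30 − 2 = 28 degrees of freedom. The following are assumptions: each mode is zero with probability z, otherwise 100 × Beta(0.8, 6), whose mean is 0.8/6.8 = 11.8%; the modes are independent within patient; both modes have the same non-zero distribution.

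| Outcome, zeros in FreeO2 against control | t coverage | t power | Rank permutation power |
|---|---|---|---|
| <85%: 50/70/80% against 95% | 93/92/90% | 84/48/20% | 97/69/31% |
| <85%, less skewed, Beta(3, 22.5), same mean | 95/94/93% | 96/63/34% | 98/67/33% |
| <88%: 10/20/30% against 80% | about 95% | 91/84/71% | 98/96/89% |

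Repeat simulations of the first row agree to within 3 points. When both modes share one distribution, with 50/70/90% zeros, the t test rejects in 4.8/4.4/1.5% of trials, so type I error is not inflated there.

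The second row shows how far the result depends on the assumed skew. The power differences are 98 − 96 = 2, 67 − 63 = 4 and 33 − 34 = −1 points. For time below 88% there is no coverage defect at all.

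**Is the rank test better in general?** Every row above changes only how many patients have a dip. The endpoint is time, so the modes may also differ in how long dips last. With the same two tests, again under assumed values:

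| Zeros (FreeO2, control) | Non-zero means | Beta first parameter | True mean difference | t power | Rank power |
|---|---|---|---|---|---|
| 60%, 60% | 20% and 5% | 0.8 | 0.4 × (20 − 5) = 6.0 | 55% | 21% |
| 50%, 50% | 20% and 5% | 0.8 | 0.5 × (20 − 5) = 7.5 | 71% | 38% |
| 70%, 80% | 20% and 5% | 3 | 0.3 × 20 − 0.2 × 5 = 5.0 | 74% | 39% |
| 60%, 60% | 20% and 5% | 3 | 0.4 × (20 − 5) = 6.0 | 81% | 42% |

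A repeat gave 57/72/74/80% against 22/39/40/41%. In these cases the rank test misses the difference about twice as often or worse in terms of power. In the three rows with equal zeros, the proportion of patients with any dip does not differ between modes either.

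The reverse case also matters. Let 60% of patients dip with mean 3% in one mode, and 20% with mean 9% in the other. Average times are equal: 0.6 × 3 = 1.8% and 0.2 × 9 = 1.8%. The rank test still rejected in 31% of trials in one run and 41% in another. It answers a different question from the one about average time.

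**The case for a change.** The best case for the concern is that the choice stands in the protocol, so an analysis plan that follows it inherits it, and that a variable with a mass at zero is not simply continuous. A separate simulation points the same way. It drew non-zero times from a lognormal with mean 8% of the period, with dips in 10–60% of FreeO2 and 2–20% of control periods. Paired-t coverage was 75–93%, one patient supplied on average 26–62% of the summed absolute differences, and t power was below Wilcoxon power in every scenario with unequal rates. Finally, a mean alone cannot show whether many patients dipped briefly or one dipped for long.

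Part of this stands. The word continuous is loose for these two outcomes, and zeros below 85% are plausible. Intervals from a t analysis could cover too little if dips are rare and strongly skewed. The lognormal model, however, also gives both modes the same non-zero distribution, so it too tests only a difference in frequency, and its dip rates and skew have no source in the documents.

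The point about many brief dips against one long one supports adding medians and the number of patients with any time below each cut-off. Nothing in Section 2.7 prevents that. It does not support replacing the mean comparison.

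**Conclusion.** The concern does not hold as an error. Section 2.7 chooses a legitimate effect measure for secondary outcomes that are themselves expressed as amounts of time. The loss attributed to it needs a t analysis that the protocol does not prescribe, together with assumed zeros and skew. Under assumptions favourable to ranks, the t test gives up 11 to 21 points of power for time below 85% (97 − 84 = 13, 69 − 48 = 21, 31 − 20 = 11) and 2 to 5 points of coverage. With milder skew the power gap is 4 points or less. If the modes differ in duration of dips, the t test leads by 33 to 39 points (55 − 21 = 34, 71 − 38 = 33, 74 − 39 = 35, 81 − 42 = 39). The documents do not settle which situation applies, so the choice is a preference between two estimands. Extra descriptive summaries would help a reader and are optional. PaCO2 is unaffected.

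### Does the four-group wording in section 2.7 discard the within-patient pairing of the crossover?

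*Protocol*

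**What the plan says.** Section 2.4 sets out a crossover with two modes and two periods. After extubation, "they will be oxygenated for 30 minutes according to FreeO 2 or control mode, in a randomized order", and then they receive the other mode for a further 30 minutes. The same section states: "Each patient will act as his own control (crossover design"). The primary variable is named in section 2.6: "The primary endpoint will be end-of-period PaCO 2". Each patient therefore contributes two values, one per period.

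Section 2.7 describes the analysis in a few lines. It opens with "Mean differences will be used for all of the outcomes since they are continuous" and continues "taking into account the crossover design (analyses with four groups"). It ends: "Analyses to assess period, time and carryover effects will be done".

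The sample size text in section 2.3 reads "empirical sample size will be set at 15 patients to detect a PaCO 2 difference of 5 mmHg between groups". Section 3 reports the later decision "to make an amendment to the protocol in order to enlarge sample size to 30 patients", after a look at the first 15 patients was judged underpowered.

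**The concern.** A crossover with two modes and two periods has two groups of patients, one per sequence, so a count of four looks odd. The only four things available are the sequence-by-period cells, and every patient appears in two of them. An analyst who compared four cell means as if they came from four separate sets of patients would leave the between-patient spread of PaCO2 in the error term. The confidence interval for the mode effect would be too wide and a real effect could be missed, in a trial already doubled in size for lack of power.

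The closing sentence of section 2.7 adds to the unease. With one arterial gas per period, four cell means carry only three contrasts: mode, period, and one that sequence, carryover and mode-by-period interaction share. For PaCO2, time cannot be separated from period, and the carryover contrast is between patients and imprecise.

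**Working it through.** **Inputs.** From the protocol: two modes, two periods and randomised order (2.4); one PaCO2 value per period (2.5, 2.6); 15 patients, later 30, and a difference of 5 mmHg (2.3, 3). Not in the protocol, so assumed: the SD of PaCO2 (sigma), the within-patient correlation (rho), a two-sided 5% level, and 15 patients per sequence.

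**The plan's own figure.** The 15 patients cannot be reproduced. Section 2.3 calls the number empirical and gives no SD, correlation, level or power. Working backwards with a crossover t test (n - 2 degrees of freedom), 15 patients detect 5 mmHg with 80% power if the SD of the within-patient difference is at most about 6.4 mmHg, and 30 patients if it is at most about 9.4 mmHg. Neither figure bears on whether the pairing is kept.

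**What four cells imply.** Write A for FreeO2 and B for control. The cells are AB1, AB2, BA1 and BA2 (sequence, then period). The mode effect, B minus A, is

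½(AB2 + BA1 - AB1 - BA2) = ½[(AB2 - AB1) - (BA2 - BA1)].

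The right-hand side compares mean within-patient period differences between the two sequences, which is the standard crossover estimate. Four cell means therefore give the paired point estimate. Only the standard error depends on whether the analysis recognises that AB1 and AB2 come from the same patients, and likewise BA1 and BA2.

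**The usual crossover model is itself a four-cell model.** Take an intercept plus indicators for mode (B), period (2) and sequence (BA). The rows are AB1 (1,0,0,0), AB2 (1,1,1,0), BA1 (1,1,0,1) and BA2 (1,0,1,1). Subtracting the first row leaves a 3×3 block with determinant -2, so the rank is 4: four parameters for four cell means. Adding a random patient effect gives the textbook mixed model, and it is an analysis of four groups that takes the crossover into account.

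**Standard errors.** With 15 patients per sequence:

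- patient effect kept: SE = sigma × sqrt((1 - rho)/15)
- cells treated as independent: SE = sigma / sqrt(15)
- ratio: 1/sqrt(1 - rho), which is 1.20, 1.41, 1.83 and 2.24 at rho 0.3, 0.5, 0.7 and 0.8.

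**Numerical check.** One simulated trial of 30 patients (sigma 6 mmHg, rho 0.7, true effect 5 mmHg):

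| Analysis | Estimate | SE |
|---|---|---|
| Four cells with patient random effect | 4.43 | 0.620 |
| Within-patient period differences | 4.43 | 0.620 |
| Four cells as independent samples | 4.43 | 1.434 |

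The first two agree. The ratio in this single sample, 1.434/0.620 = 2.31, differs from the expected 1.83 by sampling variation.

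**Which row does the protocol describe?** The parenthesis is attached to a clause saying the crossover design is respected, and section 2.4 says patients serve as their own controls. The protocol's use of the word group does not imply separate patients either: section 2.3 speaks of a difference between groups where the groups are two modes given to the same people. No section names an unpaired test, an analysis of variance on independent groups, or a model without a patient term. The text fits the first two rows; the third has to be read into it.

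**Carryover and time.** The between-patient carryover contrast has SE = sqrt(2 × sigma² × (1 + rho) × 2/15). For sigma 4 and rho 0.5 this is sqrt(6.4) = 2.5 mmHg; for sigma 6 and rho 0.7 it is sqrt(16.32) = 4.0 mmHg. The carryover detectable with 80% power is 7.3 to 11.7 mmHg, so the test is weak. Section 2.7 says only that carryover will be assessed; it does not make the primary result depend on the test. On time, section 2.7 covers all outcomes, and section 2.5 provides continuous recording of saturation, heart rate and oxygen flow within each period. Time can be studied there even though it cannot be separated from period for PaCO2.

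**The case for a change.** The best counter-argument is that the parenthesis is the only description of how the crossover is handled, and it mentions neither a within-patient difference nor a patient term. The favourable reading supplies that term. An analyst who took the parenthesis on its own could run a four-group analysis of variance. The cost would then be real: an effect with 80% power in the paired analysis would have about 53% in the four-group contrast and 31% in a four-group F test at rho 0.5. The variance would double (1/(1 - 0.5) = 2), so 30 patients would be worth 15 and the extension would be cancelled.

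That arithmetic is correct, but it belongs to an analysis the protocol does not state. Reaching it means setting the parenthesis against the clause it explains and against section 2.4. What stands is that the phrase is terse and does not define the four groups. A missing model name or patient term is detail commonly left to the SAP, which is not shown.

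It is also true that no SAP can free the PaCO2 carryover contrast from sequence and interaction, and that its test is weak. Both are general properties of a two-by-two crossover and not something section 2.7 misstates. The lack of a described washout between periods is a separate design matter and says nothing about pairing.

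**Conclusion.** The concern does not hold. The natural meaning of the four groups is the four sequence-by-period cells, and an analysis of those cells that respects the crossover gives the same estimate and standard error as the paired analysis (0.620 by both routes in the simulated trial). The inflation of 1.20 to 2.24 for rho from 0.3 to 0.8, and the power losses that follow, arise only if the cells are treated as independent samples, which the protocol nowhere says. The equality of the two analyses is shown for complete data, 15 patients per sequence and one value per period; sigma and rho affect only the size of the hypothetical loss. The carryover and time remarks identify limits of the design, not an error in the plan. A phrase defining the four groups would help a reader, but its absence is not a fault of analysis.
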